# Protocol ION-01-ALKS 4230

### Protocol ION-01-ALKS 4230

ICH	International Conference on Harmonization
ICU	Intensive Care Unit
IFN	Interferon
IL-2	Interleukin-2
IL-2R	Interleukin-2 Receptor
INR	International Normalized Ratio
ir	Immune-Related
irORR	Immune-Response Overall Response Rate
irRC	Immune-Related Response Criteria
IV	Intravenous or Intravenously
LDH	Lactate Dehydrogenase
λ_z	Terminal Elimination Rate Constant
MAX	Maximum
MEDDRA	Medical Dictionary for Regulatory Activities
MIN	Minimum
MTD	Maximum Tolerated Dose

Abbreviation	Definition
NCI	National Cancer Institute
NK	Natural Killer [Cells]
N/A	Not Applicable
ORR	Overall Response Rate
PCS	Potentially Clinically Significant
PD	Progressive Disease
PD-1	Programmed Death Receptor-1
PD-L1	Programmed Death Ligand-1
PFS	Progression-Free Survival
PR	Partial Response
РТ	Preferred Term
PTT	Partial Thromboplastin Time
Q3W	Every 3 Weeks
QTCF	QT Interval Corrected by The Fridericia Correction Formula
RCC	Renal Cell Carcinoma
R _{CD8}	Ratio of Cd8 Cells To T _{regs} (Day 1 Pre-Infusion As Baseline Levels)
R _{CD8, max}	Maximum R _{CD8}
RECIST	Response Evaluation Criteria in Solid Tumors
iRECIST	Immune Response Evaluation Criteria in Solid Tumors
R _{NK}	Ratio of Nk Cells to T _{regs} (Day 1 Pre-Infusion As Baseline Levels)
R _{NK, max}	Maximum R _{NK}
RP	Relative Percentage
RP2D	Recommended Phase 2 Dose
SAE	Serious Adverse Event
SAP	Statistical Analysis Plan
SD	Stable Disease
SE	Standard Error
SI	Standard International System of Units
SOC	System Organ Class
SOP	Standard Operating Procedure

Abbreviation	Definition
T _{1/2}	Terminal Elimination Half-Life
TEAE	Treatment-Emergent Adverse Event
TLF	Table, Listing and Figure
T _{MAX}	Time to C _{max}
TNF	Tumor Necrosis Factor
T _{CD8, MAX}	Time to Maximum R _{CD8}
T _{NK, MAX}	Time to Maximum R _{NK}
TT _{REGS}	Regulatory T Cells
TSH	Thyroid-Stimulating Hormone
ULN	Upper Limit of Normal
US	United States
VS	Versus
V _{SS}	Steady-State Volume of Distribution
Vz	Terminal Volume of Distribution
WHO	World Health Organization

1. INTRODUCTION

This statistical analysis plan (SAP) describes the statistical methods and data presentation to be used for analyzing and reporting efficacy and safety data for study ION-01-ALKS 4230. This document has been prepared based on the Alkermes ION-01-ALKS 4230 study protocol (dated 29 Oct 2018).

1.1. Study Objectives

1.1.1. Primary Objective

The primary objective of this study is to estimate the response rate to ALKS 4230 in combination with pembrolizumab in patients with Squamous Cell Carcinoma of the Head and Neck (HNSCC) who have previously received anti-programmed cell death protein 1 (anti-PD-1) or anti-programmed cell death ligand-1 (anti-PD-L1) (henceforth referred to as PD-[L]1) therapy but who have not achieved a complete remission (CR). The primary objective will be assessed for the following 2 groups:

- Group 1: Patients with stable disease (SD), defined as ≥12 weeks of SD per Response Evaluation Criteria in Solid Tumors (RECIST) v1.1 criteria, or patients with partical response (PR) with no further reduction in tumor size or response (ie, PR and not improving further) for ≥8 weeks on prior anti-PD-(L)1 therapy
- Group 2: Patients with PD (progressive disease) with no prior response to anti-PD-(L)1 therapy after ≥ 8 weeks on anti-PD-1 therapy or patients currently with PD after prior achievement of a best response of SD or PR and after ≥ 8 weeks on anti-PD-(L)1 therapy

1.1.2. Secondary Objectives

- To evaluate the duration of response (DOR), progression-free survival (PFS), time to progression (TTP), and overall survival (OS) of patients with advanced or recurrent HNSCC receiving pembrolizumab plus ALKS 4230
- To evaluate the safety and tolerability of pembrolizumab plus ALKS 4230

1.1.3. Exploratory Objectives

- To evaluate whether assessment of pretreatment biopsies from patients who have failed to achieve a CR on therapy with anti-PD-(L)1 can identify a subset of patients who are likely to respond to the addition of ALKS 4230
- To evaluate whether a second biopsy, will predict response or failure to the addition of ALK S 4230

1.2. Summary of the Study Design

The study will assess the antitumor efficacy of ALKS 4230 in combination with pembrolizumab in patients with advanced, recurrent, and/or HNSCC on treatment with an anti-PD-(L)1 antibody (pembrolizumab or nivolumab) without having achieved a CR.

The study is a multi-center, Phase 2, open-label therapy study in collaboration with ION. Patients must have received anti-PD-(L)1 therapy prior to enrollment into the study. After enrollment in the study, ALKS 4230 with pembrolizumab will be administered to 4 cohorts of patients with advanced, recurrent, and/or metastatic HNSCC who have received anti-PD-(L)1 therapy whose current response is as follows:

- Cohort 1: SD, defined as ≥ 12 weeks of SD per RECIST criteria
- Cohort 2: PR with no further reduction in tumor size or response for ≥8 weeks (ie, PR and not improving further)
- Cohort 3: PD with no prior response to anti-PD-(L)1 therapy after ≥8 weeks on anti-PD-(L)1
- Cohort 4: Current PD after prior achievement of best response of SD or PR and after ≥8 weeks on anti-PD-(L)1 therapy

Patients will be administered the combination of ALKS 4230 and pembrolizumab. For simplification, the 4 cohorts of patients will be combined into 2 arms:

- Group 1 will consist of all patients with current SD or PR (Cohorts 1 and 2) who are not progressing or further demonstrating reductions in tumor size.
- Group 2 will consist of patients with PD (Cohorts 3 and 4).

Baseline tumor biopsy will be required at the time of study entry after screening procedures have been completed and prior to first administration of combination regimen to assess each patient's tumor characteristics in an effort to identify patients with tumors that may have limited pembrolizumab efficacy or potential response to anti-PD-1/ALKS 4230 combination. Tumors will be assessed for quantity and character of tumor-infiltrating T cells and other leukocytes, and for quantitative assessment of PD-L1 expression, gene signatures that correlate with response or lack of response Patients will also have a post-treatment (second) biopsy at C1D12, or at any time from C1D8 through C1D19, to assess whether the addition of ALKS 4230 to the treatment regimen alters the TME and what changes on therapy (immunopharmacodynamics) predispose to responses to the combination.

If unexpected, unacceptable AEs are considered to be related to concurrent administration of ALKS 4230 and pembrolizumab, the PI, participating site PIs, the ION Coordinating Center PI and staff, and representatives from Alkermes will consider revising the protocol eligibility

requirements to decrease the likelihood of toxicities or may consider allowing the study to proceed as designed given the risk/benefit ratio for this population.

[figure not shown]
Study design schematics are provided in Figure 1 and Figure 2.

Figure 1:Study Design Schematic 1

Abbreviations: CR=complete remission; HNSCC=squamous cell carcinoma of the head and neck; PD=progressive disease; PD-(L)1=programmed cell death ligand-1; PR=partial response; SD=stable disease; Q3W=every 3 weeks

Figure 2:Study Design Schematic 2

Abbreviations: IV=intravenous; Q3W=every 3 weeks

Note: Pembrolizumab regimen is as follows: 200 mg once Q3W by IV infusion; ALKS 4230 regimen is as follows: 3 μ g/kg, given daily on 5 consecutive days on Days 1 through 5 of the first week of each 3 -week treatment cycle.

1.3. Study Endpoints

1.3.1. Primary Efficacy Endpoint

The primary objective of this study is to estimate the response rate to ALKS 4230 in combination with pembrolizumab in patients with HNSCC who have previously received anti-PD-(L)1 therapy but who have not achieved a CR. The primary objective will be assessed for the following 2 groups:

- Group 1: Patients with SD, defined as ≥12 weeks of SD per RECIST v1.1 criteria, or patients with PR with no further reduction in tumor size or response (ie, PR and not improving further) for ≥8 weeks on prior anti-PD-(L)1 therapy
- Group 2: Patients with PD with no prior response to anti-PD-(L)1 therapy after ≥8 weeks on anti-PD-1 therapy or patients currently with PD after prior achievement of a best response of SD or PR and after ≥8 weeks on anti-PD-(L)1 therapy.

The primary efficacy endpoint is the rate of new or improved antitumor response (hereafter referred to as objective improvement) after the addition of ALKS 4230 treatment in patients receiving ongoing anti-PD-1 therapy but who have not achieved a CR. Antitumor activity will be measured by radiological assessment compared to screening. Antitumor response rate of subsets of patients will be based on disease status (defined by PR, SD, or PD based on RECIST v1.1, determined by tumor imaging scans) at screening.

[figure not shown]
An objective improvement for patients within Group 1 (Cohorts 1 and 2) is defined as:

- SD at screening that improves to PR or CR
- PR at screening that improves to CR

An objective improvement for patients within Group 2 (Cohorts 3 and 4) is defined as:

• PD at screening that improves to PR or CR

Baseline scans must be completed within 28 days before the start of treatment. Scans are to be completed according to the time points indicated in the Schedule of Assessments (Table 4 in the protocol). Patients whose response converts from PD or SD to PR or from PR to CR will have a confirmatory scan for tumor assessments 6 weeks after the response-defining scan. Thereafter, timing of tumor assessments will depend on whether or not the patient continues with study drugs.

Patients may receive study drug while waiting for confirmation of PD if they are clinically stable as defined by the following criteria:

- Absence of signs and symptoms (including worsening of laboratory values) indicating disease progression
- No decline in ECOG Performance Status
- Absence of rapid progression of disease
- Absence of progressive tumor at critical anatomical sites (eg, cord compression) requiring urgent alternative medical intervention

1.3.2. Secondary Efficacy Endpoints

The secondary objectives are to evaluate the DOR, PFS, TTP, rate of non-progression at 6 months, and OS of patients with advanced or recurrent HNSCC receiving pembrolizumab plus ALKS 4230 and to evaluate the safety and tolerability of pembrolizumab plus ALKS 4230. Secondary efficacy endpoints in this study include:

- DOR, PFS, TTP, rate of non-progression at 6 months, and OS
- Antitumor response rate of subsets of patients based on disease status (PR, SD, or PD) at screening
- Antitumor activity as measured by radiological assessment compared to screening

1.3.3. Exploratory Endpoints

[figure not shown]
The exploratory objectives are:

- To evaluate whether assessment of pretreatment biopsies from patients who have failed to achieve a CR on therapy with anti-PD-(L)1 can identify a subset of patients who are likely to respond to the addition of ALKS 4230
- To evaluate whether a second biopsy, **and the second biopsy**, **and th**

2. SAMPLE SIZE AND STATISTICAL POWER CONSIDERATION

This study plans to enroll efficacy evaluable patients in Groups 1 and 2,

In the long-term follow-up analysis of the KEYNOTE-012 trial of single agent pembrolizumab, which was conducted in 192 patients with HNSCC, the objective improvement rate was 18% (95% CI, 13% to 24%) (Mehra et al, 2018ⁱ). Among the subset of patients achieving a response, the median time to objective improvement was 2 months (range: 2 to 17 months).

3. DATA ANALYSIS

3.1. General Statistical Methodology

Baseline for efficacy or safety analysis is defined as the last non-missing assessment before the first dose of study drug in ION-01-ALKS 4230 study on Day 1, and it will be used for all efficacy and safety analysis unless specified otherwise.

In general, summary statistics (n, mean, standard deviation, median, minimum and maximum for continuous variables, and number [%] of patients in each category for categorical variables) will be provided by group for all variables. Time-to-event variables will be summarized by Kaplan-Meier plots, medians, and ranges. The data will be tabulated and analyzed with respect to patient enrollment and disposition, demographic and baseline characteristics, prior and concomitant medications, efficacy, and safety measures. Source data for the summary tables and statistical analyses will be presented as patient data listings. All statistical tests and CIs, unless stated otherwise, will be 2-sided and will be set at α =0.05.

3.2. Definitions of Analysis Populations

3.2.1. Efficacy Evaluable Population

The Efficacy Evaluable Population will include all patients who have received at least 1 dose of both study drugs and have minimum of one post-baseline scan. The Efficacy Evaluable Population will be characterized by groups (Group 1 and Group 2) and overall for analysis of all efficacy endpoints.

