#### Safety Assessments:

- Adverse events
- Physical examination and electrocardiogram findings
- Vital signs (ie, blood pressure, pulse, respiratory rate, and body temperature)
- Clinical laboratory parameters (ie, complete blood count with differential, complete serum chemistry, and urinalysis)

Statistical Methods: For all applicable parameters, descriptive statistics will be provided.

Efficacy: Response to treatment will be evaluated using both Response Evaluation Criteria in Solid Tumors v1.1 and immune-related response criteria. For patients with objectively measurable disease, response to therapy, DOR, PFS, and OS will be calculated.

Primary efficacy endpoint will be evaluated in the Efficacy Evaluable population (all patients who received at least 1 dose of both study drugs) for each group separately and overall. The rate of objective improvement after continued anti-PD-1 therapy with ALKS 4230 will be summarized by groups (Group 1 and Group 2) and overall population with descriptive statistics. The analysis of objective response using an exact binomial test will be conducted separately for each group and overall; the 95% confidence interval will be reported.

Secondary efficacy endpoints will be evaluated in the Efficacy Evaluable population (Group 1 and Group 2).

DOR and TTP will be calculated and summarized by group and overall. PFS and OS curves will be plotted by group and overall using the Kaplan-Meier (KM) approach. The median survival time (if applicable) and its 95% CI for PFS and OS will be reported. The PFS and OS rates at 6 and 12 months will be estimated using the KM approach.

The objective response rate will be summarized for each of the 4 cohorts.

The percentage change from baseline in target lesions will be summarized by groups and overall.

Safety: The incidence of TEAEs will be summarized for the Safety Population, defined as all patients who received at least 1 dose of investigational combination, each group and overall, by severity, and by relationship to study drug as assessed by the Investigator. Similar tables will be prepared for SAEs, TEAEs leading to discontinuation, as well as additional categories of AEs as defined in the SAP.

Adverse event severity will be graded according to the CTCAE v5.0 and terms recorded on the CRFs will be mapped to preferred terms using MedDRA version 21.

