#### **13.2.1.** Study Populations

#### **13.2.1.1.** Efficacy Evaluable Population

All patients who received at least 1 dose of both study drugs will be included in the analysis of efficacy, regardless of the duration of treatment. The Efficacy Evaluable populations will be characterized by groups (Group 1 and Group 2) and overall for analysis of all efficacy endpoints.

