#### 13.4.2. Secondary Efficacy Analysis

Secondary efficacy analysis will be evaluated on the Efficacy Evaluable patients.

DOR and TTP will be calculated and summarized by group and overall. Patients with missing response data will be considered non-responders and excluded from the DOR analysis. PFS and OS curves will be plotted by group and overall using the Kaplan-Meier approach. The median survival time (if applicable) and its 95% CI for PFS and OS will be reported. The PFS and OS rate at 6 and 12 months will be estimated using the Kaplan-Meier approach.

The objective response rate will be summarized for each of the 4 cohorts.

The percentage change from baseline in target lesions will be summarized by group and overall.

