3.11. Efficacy Analyses

3.11.1. General Considerations

All statistical analyses will be performed at the 5% significance level. All confidence intervals will be 2-sided 95% confidence intervals. Efficacy analyses will be carried out using the Efficacy Evaluable Population. Response to treatment will be evaluated using RECIST v1.1.

Summary statistics (n, mean, standard deviation, median, minimum and maximum for continuous variables, and number [%] of patients in each category for categorical variables) will be provided for all variables. Time-to-event variables will be summarized by Kaplan-Meier plots, medians, and ranges. Data from all study centers will be combined for analysis. No adjustments for multiple comparisons will be applied.

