Progression-free survival (PFS) is defined as the time from the first dose to the first documentation of objective tumor progression, start of alternate therapy or death due to any cause. Patients who do not have disease progression or have not died will be censored at the last known time that the patient was progression free. If a patient begins a new anticancer treatment (either systemic or local) prior to documented progression or death, or if a patient is removed from the study due to undocumented clinical disease progression, then the patient will be censored at the last assessment where the patient was documented as progression free prior to the intervention. Patients with 2 or more consecutive missing response assessments prior to a visit with documented progression (or death) will be censored at the last date of tumor assessment when the patient was documented to be progression free. The detailed censoring rules for PFS is in section 6.2.2.

Progression-free survival will be calculated as follows (in weeks):

(date of disease progression/death – first dose date +1)/7

The survival distribution of PFS will be estimated using Kaplan-Meier methodology. The median PFS will be provided along with the two-sided 95% CIs based on the Efficacy Evaluable population. In addition, Kaplan-Meier curves will be provided. The 6-month PFS rate will be estimated using the Kaplan-Meier estimate.

• Time to Progression:

Time to progression (TTP) is defined as the time from the first dose to the confirmed tumor progression. All events of disease progression will be included regardless of whether the patient discontinued the study drug. If the patient has not experienced disease progression, the patient's data will be censored at the date of last disease assessment. Data for patients without any disease assessments performed after the first dose will be censored at the date of first study drug.

The TTP will be calculated as follows (in weeks):

(date of disease progression – date of first dose + 1)/7

TTP will be analyzed by Kaplan-Meier methodology. Median TTP will be calculated and 95% confidence interval for median TTP will be presented.

• Overall Survival:

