5. CHANGES IN CONDUCT OR PLANNED ANALYSES FROM THE PROTOCOL

There are no changes made to the statistical methods specified in the ION-01-ALKS 4230 study protocol (dated 29 Dec 2018).

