5.1. Revisions and/or clarification of definitions in SAP

Protocol Definition	SAP definition
Efficay Evaluable Population All patients who received at least 1 dose of both study drugs	Efficacy Evaluable Population All patients who received at least 1 dose of both study drugs and have minimum of one post-baseline scan

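### The SAP's added post-baseline scan requirement removes never-scanned patients from every efficacy analysis, which can only hold or raise the primary rate and drops early deaths from PFS and OS

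*SAP*

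**What the plan says.** Protocol 13.2.1.1 sets the population: "All patients who received at least 1 dose of both study drugs will be included in the analysis of efficacy", however long they were treated. The statistical methods part of the synopsis gives the same rule: "Primary efficacy endpoint will be evaluated in the Efficacy Evaluable population (all patients who received at least 1 dose of both study drugs").

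SAP 3.2.1 defines the population of the same name as "all patients who have received at least 1 dose of both study drugs and have minimum of one post-baseline scan" and applies it to all efficacy endpoints. SAP 3.11.1 repeats the scope: "Efficacy analyses will be carried out using the Efficacy Evaluable Population". SAP 3.11.2 uses it for the primary rate, and SAP 3.11.3 names it for DOR and PFS.

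SAP 5.1 shows the protocol and SAP definitions side by side, the latter being "All patients who received at least 1 dose of both study drugs and have minimum of one post-baseline scan", and gives no reason for the difference. SAP 5, directly above, states: "There are no changes made to the statistical methods specified in the ION-01-ALKS 4230 study protocol".

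Two rules on patients without assessments also matter. Protocol 13.4.2 says: "Patients with missing response data will be considered non-responders and excluded from the DOR analysis". For TTP, SAP 3.11.3 says: "Data for patients without any disease assessments performed after the first dose will be censored at the date of first study drug".

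**The concern.** Whether a patient gets a post-baseline scan is known only after treatment starts, and it can depend on how the patient fares. Death, rapid decline, toxicity and early withdrawal are all reasons for having none. Selecting the analysis set on that condition is selection on something close to the outcome.

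The trial has a single arm, and its main result is a proportion with an exact interval. No control arm shares the selection, so the denominator is part of the result.

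PFS and OS start at first dose, but membership requires reaching a scan that protocol 8.3.10 and Table 4 plan for week 6 (±7 days); protocol Table 5 and the footnote to protocol Table 7 put it at week 9. A patient who dies unscanned before then is an event by definition but is not in the set. OS needs no imaging at all, so the scan condition serves no measurement purpose there.

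**Working it through.** **Inputs.** From the documents: a reference response rate of 18% (95% CI 13% to 24%, 192 patients; SAP 2); a Clopper-Pearson 95% interval for the primary rate (SAP 3.11.2); and a median survival of 6 to 9 months for recurrent or metastatic disease (protocol 5.1). Group sizes are blacked out and the share m of dosed but never-scanned patients is not given, so every n, m and responder count below is an assumption. The documents show no figure for the effect of this restriction. As a check of the interval method on the reference rate, Clopper-Pearson gives 17.7% (12.6 to 23.9) for 34/192 and 18.2% (13.0 to 24.4) for 35/192; both round to the stated figures.

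**Primary rate.** With r responders among n dosed patients, u of them never scanned, the protocol rate is r/n and the SAP rate is r/(n−u). The ratio is n/(n−u) = 1/(1−m), which is never below 1. The two rates are equal only if r = 0 or u = 0.

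For a true 18%:
- m = 2%: 18/0.98 = 18.4%
- m = 5%: 18/0.95 = 18.9%
- m = 10%: 18/0.90 = 20.0%

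With an assumed n = 40 and r = 7:

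| Never scanned | Rate | 95% CI |
|---|---|---|
| 0 (protocol set) | 7/40 = 17.5% | 7.3 to 32.8 |
| 2 | 7/38 = 18.4% | 7.7 to 34.3 |
| 4 | 7/36 = 19.4% | 8.2 to 36.0 |

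The shift is 0.9 to 1.9 points, against an interval 32.8 − 7.3 = 25.5 points wide.

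**PFS.** SAP Table 5 counts a death before the first progression assessment as an event. The population drops that patient if no scan was done. The loss covers only deaths before two missed assessments, because the same table censors later ones.

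**OS.** An unscanned death is an event in SAP Table 3 but falls outside the population. Unscanned survivors go too, including those who would have been telephoned every 12 weeks under footnote c of protocol Table 4, and that acts the other way. If S is survival at 12 months among all treated patients and Su that of the unscanned, the SAP set estimates S* = (S − m·Su)/(1 − m), which exceeds S only if Su < S. With exponential survival, S = exp(−ln 2 × 12/median) = 25.0% (median 6 months) or 39.7% (median 9 months).

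| m | Survival of unscanned at 12 months | 25.0% reads | 39.7% reads |
|---|---|---|---|
| 5% | 0% | 26.3% | 41.8% |
| 5% | same as all | 25.0% | 39.7% |
| 5% | 50% | 23.7% | 39.1% |
| 10% | 0% | 27.8% | 44.1% |
| 10% | 50% | 22.2% | 38.5% |

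For scale, the same model puts 14.7% (median 6 months) or 10.1% (median 9 months) of dosed patients dead before week 6. Removing all of them would move 6-month OS from 50.0% to 58.6%, or from 63.0% to 70.1%. This assumes that the background death rate applies from day 1 and that none of those patients had an earlier scan.

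**TTP.** The rule that censors patients without post-dose assessments at first dose can match nobody in a set that requires a post-baseline scan. It fits the protocol population.

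**The case against.** The best defence is in the protocol itself. Section 8.3.10.1 limits evaluability for objective response to patients with measurable disease, at least one cycle and a re-evaluation, so for response the SAP moves towards a definition that already exists. That stands in part: the protocol holds two possible denominators and must reconcile them. But 13.2.1.1 is the named analysis set, 8.3.10.1 keeps patients with objective progression before the end of Cycle 1, and it says nothing about PFS, TTP or OS.

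The effect may also be small. Footnote t of protocol Table 4 asks for a scan at discontinuation without confirmed progression, and footnote s allows earlier scans if clinically indicated; both reduce m among living patients. They also leave early deaths a larger share of those never scanned. The 18% is single-agent response in another trial, and the 6 to 9 month median may not fit this selected population, least of all Group 1. These limits on size stand.

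A responder followed only by clinical examination, which protocol 8.3.10.3 allows for lesions that cannot be imaged, could be dropped and lower the rate. That exception is remote, because protocol 11.1 and SAP 1.3.1 specify radiological assessment.

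Some points are minor. The TTP rule is redundant and changes no result. The early-death row in SAP Table 5 still works for a patient scanned as stable who then dies. SAP 5.1 discloses the new definition, so its clash with SAP 5 is editorial. The non-responder rule in protocol 13.4.2 sits beside the DOR text, so carrying it to the primary rate is a reasonable inference rather than an explicit instruction.

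Finally, the population counts (SAP 3.3) and the death listing (SAP 3.13.3) would let a reader rebuild the all-treated response rate and part of OS. No all-treated efficacy analysis is planned, however.

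**Conclusion.** The concern holds. The SAP departs from the protocol's efficacy population without a reason and extends a scan condition to endpoints where nothing in the documents supports it. For the primary rate the effect has one direction, upward or none, apart from the remote clinical-examination case; by the illustrations above it is about one point at 5% unscanned and two at 10%. For PFS, early unscanned deaths are lost, so bias is upward to the extent that unscanned patients are such deaths. For OS, upward bias is likely but depends on unscanned patients surviving worse than average; with average survival there is no change, and with better survival the estimate falls. The textual mismatch is certain. The size is not, because m and the group sizes are unknown.

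**What to change.** - In SAP 3.2.1 and 5.1, restore the protocol population (at least one dose of both study drugs, including dosed patients later replaced under protocol 7.4) for the primary rate, PFS, TTP and OS.
- In SAP 3.11.2, state that patients with no post-baseline scan are non-responders and stay in the denominator, consistent with protocol 13.4.2.
- Keep the scanned set as a labelled sensitivity analysis for response only, and state how the evaluability term in protocol 8.3.10.1 relates to 13.2.1.1.
- Report by group how many treated patients were never scanned, and why.
- Align the no-changes statement in SAP 5 with SAP 5.1.

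The cost is SAP wording and one extra table. The reported rate may become slightly less favourable. No clinical procedure changes.
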